### Determination of metabolic profile

The determinations for obtaining the lipid and glycemic profile were carried out through standard techniques with the automatic analyzer of clinical chemistry BA 400 (BioSystems) in the SYNLAB laboratories (Diagnosticos Globales S.A.U., Badajoz, Spain).

### Determination of immuno-neuroendocrine parameters

For the determination of the pro-inflammatory and anti-inflammatory cytokines studied (IL-1 $\beta$  and IL-10), an instrument based on flow cytometry was used: the Lu-minexTM 200 System instrument (Luminex Corporation, Texas, USA) using the Pro-cartaPlex TM Multiplex Immunoassay. Catecholamines such as dopamine, epinephrine and norepinephrine and also stress hormones like serotonin, cortisol, corticotropin-releasing hormone (CRH) and the adrenocorticotropic hormone (ACTH) were analyzed by competitive inhibition enzyme immunoassays (ELISA), using respectively: Dopamine Research Immunoassay, General Epinephrine (EPI) RD-EPI-Ge-96T and General Noradrenaline (NE) RD-NE-Ge-96T, General 5-Hydroxytryptamine (5-HT) RD-5-HT-Ge, The DetectX Cortisol Immunoassay Kit, Human Corticotropin Releasing Hormone (CRH) RD-CRH-Hu (Kelowna, BC, V1W 4V3, Canada) and Human ACTH (Adrenocorticotropic Hormone) ELISA Kit (Elabscience, USA). To determine immuno-globulin A in saliva, samples were analyzed by indirect enzyme immunoassay kit through the Salivary Secretory IgA Kit (Salimetrics LLC, USA). The procedures followed the instructions of the manufacturers, and the findings were measured using an ELISA auto analyzer to quantify color intensity (Sunrise, Tecan, Männendorf, Switzerland).

### **Statistical Analysis Plan (SAP):**

Statistical analysis was performed with IBM statistics SPSS v20.0 software (SPSS Inc., Chicago IL, USA). To verify the normality of the data, the Shapiro-Wilk test was performed. The repeated two-way analysis of variance (ANOVA) was used, followed by Student's paired and unpaired t-tests to analyze the intervention effect. The values were expressed as mean  $\pm$  standard deviation (SD) and the significance level was considered when  $p<0,05$ .

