**Design:**

This investigation was a triple blinded, randomized, placebo-controlled pilot study designed to identify the possible differing effects of the synbiotic Gasteel Plus® supplementation between sedentary individuals and soccer players. Subjects were asked to maintain their regular lifestyle and the participants were prohibited from consuming probiotics, prebiotics or fermented products (yogurt or other foods) to avoid unnecessary interference during the experimental periods. Presenting injury or illness would result in exclusion from the study. All participants were also asked to provide written informed consent before participating in the study, which had been previously approved by the ethics committee of the Catholic University of Murcia (Spain) following current legislation (CE031810).

On two separate days, the "baseline-tests" and "final-tests" were conducted. All participants performed a series of tests, before which they had to fast. The order and schedule (8 am) of the tests was the same for the "final-test" and the same materials and procedures were used. A period of 30 consecutive days elapsed between the base-line and final tests, during which the participants had to ingest their supplement (synbiotic or placebo). Accelerometers were distributed one week prior to the baseline test and the week after the final test. Blood and saliva sampling were taken early in the morning and questionnaires were filled out on the two testing days. The treatment was carried out during the last fortnight of May 2019 and the first fortnight of June of the same year, coinciding with situations of possible physical and mental stress in both participant groups, being at the end of an examination period, as well as the end of the soccer season.

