### Results:

Among the most important results we can observe:

the sedentary group administered with placebo obtained some significant differences with respect to baseline values ( $p<0,05$ ). A decrease in calories, metabolic rate and intensity level of physical activity are reflected. The synbiotic seems to prevent this situation by avoiding the mentioned decreases and even increasing the consumption of Kilocalorie (Kcal) in sedentary individuals although without significant differences. Results from the athlete group show no significant changes ( $p>0,05$ ) in those who consumed placebo, while those who followed the protocol with the intake of the synbiotic had significant improvements in sleep efficiency and latency, as well as increases in the consumption of Kcal and METS.

The baseline values are quite similar in the sedentary and athlete groups. Only in the athletes did the synbiotic intervention significantly improve ( $p<0,05$ ) the perceived general health as determined by the SF-36 questionnaire, but no differences were found in perceived sleep quality, state anxiety, and fatigue.

No significant differences were found in the perceived stress, trait anxiety, and depression between sedentary people and athletes at basal status (before intervention). The results show a decrease in the levels of perceived stress ( $p<0.01$ ) and anxiety ( $p<0.05$ ) only in the athlete group administered with the synbiotic. Also shows a decrease ( $p<0.05$ ) in perceived depression levels in both groups (sedentary and athlete) after the synbiotic treatment. Then, training only affected the behavior in response to the synbiotic intervention in stress and particularly in anxiety ( $p<0.05$ ) also when evaluating by the two way ANOVA test). These effects were not due to a placebo effect.

The results corresponding to blood concentrations of glucose, cholesterol, and triglycerides as measurements of metabolic profile. Firstly, individuals in both the sedentary and athlete groups presented lipid and glycaemic levels compatible with normal and healthy ranges. Thus, as expected the consumption of the synbiotic did not provoke an appreciable or significant effect

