It should be noted that both groups presented healthy baseline levels of the inflammatory and immune parameters analysed. No significant differences in the IL-1 $\beta$  concentrations were observed between the sedentary and athlete groups. However, a different behaviour ( $p<0.05$ ) between the two groups was found in response to the synbiotic intervention: while the synbiotic increased ( $p<0.05$ ) the systemic concentration of IL-1 $\beta$  in the sedentary group, it slightly decreased in the soccer player group.

No significant variations (except a potential placebo effect in the sedentary group) were found in the IL-10 concentration. There were also no significant differences in the levels of immunoglobulin A between groups, or as a consequence of the intervention.

A lower concentration without significant differences were found in the dopamine concentration of the soccer players group. However, training affected the response to the synbiotic intervention ( $p<0.05$ ), since it induced a significant increase ( $p<0.05$ ) in the dopamine concentration only in the athletes. This effect cannot be attributable to a potential placebo effect of the intervention. However, the decrease ( $p<0.05$ ) in epinephrine levels in the sedentary group administered with the synbiotic compared to their basal levels could potentially be attributed to a placebo effect of the intervention. In addition, there were also no significant changes in norepinephrine. Basal concentration of serotonin was, however, higher ( $p<0.05$ ) in the athlete group than in the sedentary group, but statistical differences with the synbiotic intervention were not observed.

Finally, the results corresponding to CRH showed a lower systemic concentration of CRH than sedentary volunteers. In addition, the behaviour of CRH secretion in response to the synbiotic intervention was also different ( $p<0.05$ ) between the athlete group and the sedentary group, decreasing significantly ( $p<0.05$ ) in the sedentary group with respect to their baseline levels (as also found with the placebo) and increasing slightly in the athlete group. The latter cannot be attributable to a placebo effect of the intervention. There were no significant differences in levels of cortisol and ACTH between groups or as a consequence of the intervention.

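### No synbiotic-versus-placebo comparison of change is specified or reported, yet the Results conclude that effects were not placebo effects

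*Combined protocol and SAP*

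**What the plan says.** The Design section describes a randomised, placebo-controlled, triple-blind pilot in sedentary people and soccer players, measured at baseline and after 30 days. The statistical plan for the intervention is one sentence: "The repeated two-way analysis of variance (ANOVA) was used, followed by Student's paired and unpaired t-tests to analyze the intervention effect". The factors, the unpaired groups and the quantity tested (change or final value) are not named.

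The Results then make these statements about supplement and placebo:

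- **Activity, sedentary group.** Declines from baseline are reported on placebo, and "The synbiotic seems to prevent this situation by avoiding the mentioned decreases".
- **Sleep, Kcal and METs, athletes.** No significant changes are reported "in those who consumed placebo, while those who followed the protocol with the intake of the synbiotic had significant improvements".
- **Stress, anxiety, depression.** After within-group decreases and the statement that "training only affected the behavior in response to the synbiotic intervention in stress and particularly in anxiety", the paragraph ends "These effects were not due to a placebo effect".
- **Dopamine.** A rise in athletes on synbiotic is followed by "This effect cannot be attributable to a potential placebo effect of the intervention".
- **CRH.** The response is described as falling in the sedentary group, as it also did on placebo, and "increasing slightly in the athlete group. The latter cannot be attributable to a placebo effect of the intervention".

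**The concern.** Supplement is the randomised factor. Comparing change on synbiotic with change on placebo is what separates a supplement effect from anything else that happened over the 30 days. Background change is plausible here, though not certain: the Design section places treatment at the end of exams and of the season, "coinciding with situations of possible physical and mental stress in both participant groups".

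Two substitutes appear in the Results. One sets a significant within-arm change beside a non-significant one. The other compares athletes with sedentary people in their response to the synbiotic. The first does not test a difference between arms. The second compares groups that cannot be randomised and, as described, does not bring in the placebo arms. If the placebo conclusions rest on either, a reader cannot tell whether they are supported.

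**Working it through.** **Reading the comparisons.** The design has three factors: supplement, population and time. If time is one of the two factors, as a repeated-measures ANOVA implies, only one place is left for supplement and population. A single four-level group factor would be possible, but its interaction with time would not isolate the supplement. In the Results, every p-value whose comparison can be identified is either within an arm against baseline or athlete against sedentary. The one explicit ANOVA result concerns training. No synbiotic-minus-placebo result appears.

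The plan has no figure of its own to reproduce: arm sizes, means and SDs of change are not given. The calculations below are illustrations. The assumptions are n = 8 to 20 per arm, equal n, normally distributed changes with equal SD, and two-sided 0.05.

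**1. What a within-arm p-value implies between arms.** Suppose the synbiotic paired test gives statistic t1 on n − 1 df and the observed placebo mean change is zero. The between-arm statistic is then t1/√2 on 2n − 2 df.

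| n per arm | t1 at p = 0.05 | t1/√2 | df | between-arm p |
|---|---|---|---|---|
| 8 | 2.365 | 1.672 | 14 | 0.117 |
| 10 | 2.262 | 1.600 | 18 | 0.127 |
| 15 | 2.145 | 1.517 | 28 | 0.141 |
| 20 | 2.093 | 1.480 | 38 | 0.147 |

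Starting from a paired p of 0.01, the same arithmetic gives a between-arm p of 0.027 (n = 8) to 0.050 (n = 20).

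**2. How often the pattern arises with no supplement effect.** Let both arms truly change by d SD. Each paired t statistic is noncentral t with noncentrality d√n. The probability of a favourable significant result on synbiotic and a non-significant result on placebo is P(favourable significant) × P(not significant). For n = 10 and d = 0.5 this is 0.293 × 0.707 = 0.207.

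| n per arm | d = 0 | 0.2 | 0.5 | 0.8 | 1.0 |
|---|---|---|---|---|---|
| 8 | 2.4% | 6.6% | 17.8% | 25.0% | 21.7% |
| 10 | 2.4% | 7.5% | 20.7% | 23.6% | 15.8% |
| 15 | 2.4% | 9.6% | 24.6% | 14.7% | 4.8% |
| 20 | 2.4% | 11.5% | 24.6% | 7.0% | 1.1% |

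A direct between-arm test gives 2.5% in that direction throughout. In simulation with n = 10 and d = 0.5, only 11% of trials showing synbiotic significant and placebo not also had a significant between-arm test.

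**3. Athlete versus sedentary among synbiotic takers.** Let athletes change by d SD in both arms and sedentary people not at all, so the supplement does nothing. The rejection rates of the athlete-versus-sedentary test within the synbiotic arm are:

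| n per arm | d = 0.5 | d = 1.0 |
|---|---|---|
| 8 | 15.3% | 46.0% |
| 10 | 18.4% | 56.2% |
| 15 | 26.2% | 75.2% |
| 20 | 33.8% | 86.8% |

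At d = 0 the rate is 5%. In the same simulations, synbiotic versus placebo within athletes rejects in 4.7 to 5.1%, and the supplement-by-population test in 4.8 to 5.2%.

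**The case against.** The strongest reply is that this may be a reporting gap. The unpaired t-tests could include synbiotic versus placebo, and the Results present themselves as a selection, without tables. For several outcomes (SF-36, stress, dopamine) the text does not say which test produced the p-value, and it does not say whether the placebo arms entered the ANOVA. This stands: the supportable claim is that the contrast is not specified and not reported, not that it was never run. The conclusions are nevertheless stated in these documents with no between-arm result behind them.

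Other points stand in part:

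- The athlete–sedentary comparison is the declared aim. But differing effects of the supplement is a supplement-by-population question, which needs the placebo arms.
- The third illustration assumes change in athletes only, while the Design section mentions possible stress in both populations. If both change equally, that test stays at 5%.
- Stress is reported at p<0.01, so under the zero-placebo-change assumption it could survive a direct test at about the 5% level.
- If the t-tests were run only after a significant arm-by-time interaction, the pattern in the second illustration occurs in at most 2.3% of trials. The SAP does not say so.
- The authors did weigh placebo: they allow a placebo explanation for the epinephrine fall and potentially for IL-10. This shows that the placebo arms were looked at, not that the arms were compared.
- The scope of the sentence closing the stress paragraph is unclear, as is what the CRH sentence refers to. On any reading, no synbiotic-versus-placebo result is given.

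**Conclusion.** The concern holds and must be fixed. The SAP does not define the randomised comparison, the Results do not report it, and the statements that rule out placebo or suggest prevention have no between-arm test behind them in these documents. This follows from the text and does not depend on the illustrations.

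The size for this trial cannot be computed. Under the assumed arm sizes and common changes of 0 to 1.0 SD, the favourable discordant pattern occurs in about 1 to 25% of trials with no supplement effect. It exceeds the nominal 2.5% most clearly at moderate background change, and not at all when there is none. Some findings may survive a direct comparison, and the data in hand can show which.

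**What to change.** State that the supplement contrast is the test of the intervention, and name the ANOVA factors and the groups in each unpaired test. For each outcome, fit one ANCOVA of the final value on supplement, population, supplement × population and baseline value. An arm-by-time interaction or a comparison of change scores would also be valid. Report the synbiotic-minus-placebo difference with its 95% confidence interval, overall and within each population. Base any claim that training alters the response on supplement × population. Keep within-arm changes as description. Withdraw the placebo and prevention statements unless the contrast supports them. If a between-arm test was already run, report it.

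The cost is SAP wording and a re-run on data already collected, with no new participants. Because the study is complete, the re-analysis should be labelled post hoc. Some significant findings may not survive, and within-population intervals may be wide in a pilot.

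### The SAP does not name the factors of its two-way ANOVA or a treatment × population × time contrast for its stated aim, and the differing CRH response to the synbiotic is not demonstrated as reported

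*Combined protocol and SAP*

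**What the plan says.** The Design section describes a randomized, placebo-controlled pilot "designed to identify the possible differing effects of the synbiotic Gasteel Plus® supplementation between sedentary individuals and soccer players". Tests are done at baseline and after 30 days. Treatment falls at a time of possible stress for both populations, "being at the end of an examination period, as well as the end of the soccer season".

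The SAP gives the inferential analysis in one sentence: "The repeated two-way analysis of variance (ANOVA) was used", "followed by Student's paired and unpaired t-tests to analyze the intervention effect". It does not say which two factors the ANOVA has, which interaction answers the aim, or which groups the t-tests compare.

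The Results mention the ANOVA once, for stress and anxiety ("also when evaluating by the two way ANOVA test"), again without its factors. The paragraph on stress, anxiety and depression closes with "These effects were not due to a placebo effect" and names no test against placebo.

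For CRH, the Results say that the response to the synbiotic differed between athletes and sedentary people (p<0.05). They add that CRH fell significantly in sedentary people, that this fall was also seen on placebo, and that CRH rose slightly in athletes, with no p-value for the rise. The athlete rise is then said not to be a placebo effect.

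**The concern.** A differing synbiotic effect is a difference of differences: the synbiotic-minus-placebo change in athletes, less the same quantity in sedentary people. It needs the placebo arm of both populations. The SAP does not name this quantity, and no result is identified as an estimate or test of it.

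The timing makes this matter. The end of exams and the end of the soccer season could move stress-related measures differently in the two populations with no synbiotic effect at all. A comparison of populations among synbiotic recipients alone would take such drift for a differing synbiotic effect. From the text, a reader cannot tell which kind of comparison produced the reported p-values.

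The gap concerns the between-population claims. Effects within each population, which the Objective also covers, can be addressed by treatment × time in that population.

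**Working it through.** **Step 1. Match design to model.**

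| Factor | Levels | Source |
|---|---|---|
| Treatment | synbiotic, placebo (randomized) | Design |
| Population | sedentary, soccer players | Objective, Design |
| Time | baseline, final (30 days) | Design |

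Let Δ be the mean change in a cell, with A = athletes, S = sedentary, syn = synbiotic and pla = placebo. The aim corresponds to

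C3 = (Δ_A,syn − Δ_A,pla) − (Δ_S,syn − Δ_S,pla),

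which is treatment × population × time, or equivalently treatment × population on change.

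The SAP's phrase allows two readings:
- One between-subject factor plus time: C3 is absent.
- Two between-subject factors with repeated measures: C3 is available.

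The text does not settle which.

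**Step 2. Put the CRH statements into the four cells.**

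| Cell | Reported CRH change |
|---|---|
| Sedentary, synbiotic | fall, p<0.05 |
| Sedentary, placebo | fall also found (no separate p-value) |
| Athlete, synbiotic | slight rise, no p-value |
| Athlete, placebo | no value; the synbiotic rise is said not to be a placebo effect |

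The sedentary difference net of placebo is not given, and the fall is common to both arms. The athlete difference net of placebo is not given either. C3 cannot be formed from what is reported.

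**Step 3. Illustrate the consequence.** The documents give no sample size, SD or effect size, so there is no figure of theirs to reproduce. Assumptions: n = 6, 10 or 15 per cell; change scores normal with SD 1; no synbiotic effect; two-sided 0.05 (the SAP does not state sidedness).

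The placebo-free contrast is C2 = Δ_A,syn − Δ_S,syn, tested by a two-sample t on change with df = 2n − 2 and noncentrality d/√(2/n), where d is the difference in drift between populations. Example: n = 10, d = 1.0 gives 1/√0.2 = 2.236 on 18 df, rejection 0.562.

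| n per cell | Equal drift in both populations | Sedentary-only drift 0.5 SD | 1.0 SD | 1.5 SD |
|---|---|---|---|---|
| 6 | 5% | 12% | 35% | 65% |
| 10 | 5% | 19% | 56% | 89% |
| 15 | 5% | 26% | 75% | 98% |

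With the same drift in both arms of a population, C3 = (0 − 0) − (−d + d) = 0, so the three-factor contrast rejects in about 5% throughout; simulation agrees.

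**Step 4. Cost of the three-factor contrast.** In SD units, Var(C3) = 4/n and Var(C2) = 2/n, so the standard error is √2 = 1.41 times larger. The 95% half-width is t(0.975, 4n − 4) × 2/√n for C3 and t(0.975, 2n − 2) × √(2/n) for C2. Power for a 1 SD effect in athletes only uses noncentrality 1/√(4/n) on 4n − 4 df.

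| n per cell | Half-width C3 | Half-width C2 | Power of C3 |
|---|---|---|---|
| 6 | 1.70 | 1.29 | 21% |
| 10 | 1.28 | 0.94 | 34% |
| 15 | 1.03 | 0.75 | 48% |

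**The case against.** The strongest reply is that the ANOVA may already have crossed treatment with population over time. The CRH p-value would then be the right test, and only its description would be incomplete. The Results are also presented as selected highlights without tables, so the absence of a contrast there does not show that none was run. Both points stand. A reader might infer that CRH was never tested against placebo, or that the p-values came from a comparison among synbiotic recipients only. The wording is compatible with that, but the documents do not say it.

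The authors also disclose the sedentary placebo fall and limit their remark about placebo to what reads as the athlete rise. That is fair reporting, but disclosure is not a test of the difference.

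The illustration depends on unequal drift. The Design section mentions possible stress in both populations, and equal drift gives only 5%. The table therefore shows what could happen under a placebo-free test. It does not give the probability that the CRH claim is spurious.

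**Conclusion.** The concern holds in a limited form and should be fixed. Two things are established with high confidence: the SAP does not specify the contrast that its design aim needs, and no CRH comparison net of placebo between populations is reported. How the reported p-values were obtained is not known.

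For CRH, a differing synbiotic effect is not demonstrated as reported. A reader might go further and infer that the effect is absent or the claim false. The documents do not support that, because a difference arising in athletes remains possible. For stress, anxiety, IL-1β, dopamine and the athlete-only finding on SF-36 general health, the same gap is possible but cannot be verified.

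The illustrative rejection rates, 5% under equal drift and 12% to 98% under sedentary-only drift, rest entirely on assumed cell sizes and drifts and apply only if a placebo-free test was used.

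**What to change.** In the SAP, name the three factors (treatment, population, time) and make treatment × population × time, or treatment × population on change, the test of differing effects.

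In the Results:
- State which model term produced each p-value for a different response. If the ANOVA already held the three-factor term, say so and report it.
- Give the synbiotic-minus-placebo difference in change in each population, and the difference between the two, each with a 95% CI. Do this for every outcome with a between-population claim: CRH, stress, anxiety, IL-1β, dopamine and SF-36 general health. Label the analyses post hoc if they were not already run.
- Until then, word the CRH result as a between-population difference for which no comparison net of placebo is reported.

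The cost is a few lines of SAP text and an analysis of six outcomes on existing data. The price in precision is the 1.41-fold standard error and the low power shown above, so a null interaction in this pilot must not be read as no difference between populations.

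### The analysis never uses the baseline value as a covariate: this costs precision if the unnamed ANOVA factors are arm and time, and leaves the ANOVA without a synbiotic–placebo contrast if they are population and time

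*Combined protocol and SAP*

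**What the plan says.** The Statistical Analysis Plan (SAP) section is one short paragraph. After a Shapiro-Wilk check of normality it states "The repeated two-way analysis of variance (ANOVA) was used", then "paired and unpaired t-tests to analyze the intervention effect", with significance at 0.05. It does not name the two ANOVA factors, does not say whether the unpaired tests use final values or changes, and mentions no covariate.

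The Design section describes a "triple blinded, randomized, placebo-controlled pilot study" in two populations, sedentary people and soccer players. On timing it says "A period of 30 consecutive days elapsed between the base-line and final tests", and it adds that "the same materials and procedures were used" at the final test. It also says "Blood and saliva sampling were taken early in the morning and questionnaires were filled out on the two testing days". Accelerometers were worn for one week before the baseline test and one week after the final test. Each outcome therefore has one value before and one value after supplementation, obtained in the same way.

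The Results section works largely by within-arm comparison with baseline, for example "the sedentary group administered with placebo obtained some significant differences with respect to baseline values". It names the two-way ANOVA once, on whether training altered the response to the synbiotic in stress and anxiety.

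**The concern.** In a randomized trial with one baseline and one final measurement, the baseline is usually the best available predictor of the final value. Regressing the final value on baseline and arm (ANCOVA) uses that information with the slope the data support. A change score fixes the slope at 1, and a final-value comparison fixes it at 0. Either fixed choice generally gives a wider interval for the synbiotic–placebo difference.

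The cost matters most where arms are small and outcomes noisy. The documents call the trial a pilot, and many outcomes are circulating hormones and cytokines. The SAP also specifies no synbiotic-minus-placebo estimate with a confidence interval, so the randomized comparison may not be reported in usable form at all.

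**Working it through.** **Inputs from the documents.** A randomized two-arm comparison in each of two populations; one baseline and one final value; significance level 0.05 (Design and SAP sections). Two-sided testing is assumed.

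**Inputs not in the documents.** Arm size, SD, target effect and the baseline–final correlation r. There is no planned power or sample size to reproduce. Everything numerical below assumes a 0.8 SD effect, equal SDs at both times, and the r and n shown.

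**Step 1: what the ANOVA tests if its factors are arm and time.** With two time points, the arm-by-time F equals the squared unpaired t on change. In a simulated data set with 10 per arm, both came to 0.172.

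**Step 2: large-sample variance of the between-arm estimate**, in units of 2·SD²/n:
- final value only: 1
- change score: 2(1−r)
- ANCOVA: 1−r²

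The ANCOVA/change ratio is (1−r²)/[2(1−r)] = (1+r)/2. The ANCOVA/final-value ratio is 1−r². The last two columns give n per arm for 80% power, n = 2(1.960+0.842)²V/0.8² = 24.5·V rounded up, where V is the variance above. A final-value test needs 25 at any r.

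| r | change | ANCOVA (also its ratio to final-value) | ANCOVA/change | n, change | n, ANCOVA |
|---|---|---|---|---|---|
| 0.3 | 1.40 | 0.91 | 0.65 | 35 | 23 |
| 0.5 | 1.00 | 0.75 | 0.75 | 25 | 19 |
| 0.7 | 0.60 | 0.51 | 0.85 | 15 | 13 |
| 0.8 | 0.40 | 0.36 | 0.90 | 10 | 9 |

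**Step 3: small arms.** Estimating the slope inflates the ANCOVA variance by about 1+1/(2n−4) in a two-arm model.
- 10 per arm: factor 1.0625. At r = 0.7 the variance is 0.51 × 1.0625 = 0.54, against 0.60 for change.
- 6 per arm: factor 1.125. At r = 0.8 it is 0.36 × 1.125 = 0.405 against 0.40; at r = 0.9 it is 0.19 × 1.125 = 0.214 against 0.20. The advantage has gone.

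Power in the two-arm model is shown below. For change it follows from the noncentral t; for 10 per arm and r = 0.5, the noncentrality is 0.8 × √5 = 1.79 on 18 df. For ANCOVA it is simulated, and separate runs differ by about a point.

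| n per arm | r | change | ANCOVA |
|---|---|---|---|
| 10 | 0.5 | 40% | 47% |
| 15 | 0.3 | 43% | 59% |
| 15 | 0.5 | 56% | 67% |
| 10 | 0.7 | 59% | 63% |
| 15 | 0.7 | 78% | 83% |
| 6 | 0.8 | 51% | 50% |
| 6 | 0.9 | 80% | 76% |

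**Step 4: one model over both populations.** Pooling the slope and residual variance over four cells lowers the inflation to about 1+1/(4n−6), which is 1.056 at 6 per cell. For the within-population contrast, power is then 55% (change) against 57% (ANCOVA) at r = 0.8, and 84% against 84% at r = 0.9. The small-sample penalty largely disappears.

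**Step 5: if the factors are population and time.** The ratios in Step 2 do not describe that comparison. It sets sedentary people against athletes, who were not randomized to those groups. The ANOVA then gives no synbiotic–placebo contrast, and only the unpaired t-tests could supply one.

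**The case against.** The strongest reply is that the criticised analysis is partly inferred. The SAP names no factors. The one ANOVA result cited, and the contrasts reported for IL-1β, dopamine and CRH, read at least as naturally as sedentary versus athlete. This stands, so the point has to be put conditionally. ANCOVA is also not automatically preferable between non-randomized populations that differ at baseline, as serotonin did here. The proposed model avoids that difficulty, because it estimates randomized supplement contrasts within each population and then the difference between those contrasts.

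A second reply is that the gain is assumed and not universal. This also stands. It is modest at r = 0.7, and at about 6 per arm with r of 0.8 or more a two-arm ANCOVA is no better or slightly worse. Pooling the populations removes most of that penalty.

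A reader might infer that the between-arm results are biased, or that the ANOVA mistakes regression to the mean for a treatment effect. The documents do not support this. Under randomization, a between-arm comparison of changes is unbiased on average; it is off only conditionally on a chance baseline imbalance. Regression to the mean is mainly a hazard of the within-arm paired tests on which the Results section leans. That is a separate and more serious matter.

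**Conclusion.** The point holds in a limited form. The SAP leaves a like-for-like baseline unused as a covariate. If the ANOVA is arm by time, adjustment would cut the variance of the synbiotic–placebo estimate by 10% to 35% for r from 0.8 down to 0.3, in large samples with equal SDs. Against a final-value t-test, the cut over the same r values runs from 64% down to 9%. If the ANOVA is population by time, it lacks the randomized contrast, and the gap is the missing estimate.

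The loss in this trial cannot be calculated. That the arms are small rests only on the word pilot, and r will differ between outcomes. The illustrated gains of about 4 to 16 percentage points apply to 10 to 15 per arm with r of 0.3 to 0.7. It would go too far to say that the trial lost a known amount of power, or that its between-arm conclusions are invalid. The improvement is worth making because it costs almost nothing.

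**What to change.** State which two factors the ANOVA used and whether the unpaired tests compared final values or changes. Then, for each outcome, fit one linear model of the final value on baseline value, supplement, population and supplement × population, using both populations together. Report the adjusted synbiotic-minus-placebo difference in each population and the supplement × population interaction, each with a 95% CI, as the estimates of effect. The model assumes a common baseline slope in the two populations; say so.

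Results are already reported, so this must be labelled a post-hoc re-analysis and placed beside the existing SAP text, which should not be rewritten as if this had been planned.

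The cost is one degree of freedom per model and a re-run on data already held, in the same software.
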